8.3.2 CLASSIFICATION OF AN ADVERSE EVENT

8.3.2.1 SEVERITY OF EVENT

For adverse events (AEs) not included in the protocol defined grading system, the following guidelines will be used to describe severity.

- **Mild –**
 - Events that do not interfere with the participant’s daily activities, cause significant distress, or interfere with major life functions.
 - Medication errors that require minimal or no treatment (NCC MERP categories B and C).
- **Moderate –**
 - Events that cause inconvenience, interference with functioning, disruption of usual daily activity, or greater worry or concern.
 - Medication errors that require monitoring and/or intervention to prevent harm (NCC MERP categories D and E).
- **Severe –**
 - Events that significantly interrupt a participant’s usual daily activity, cause distress, or interfere with major life functions.
 - Medication errors that prolong hospitalization, are potentially life-threatening, are incapacitating, or are fatal (NCC MERP categories F to I).

8.3.2.2 RELATIONSHIP TO STUDY INTERVENTION

All adverse events (AEs) must have their relationship to study intervention assessed by the clinician who examines and evaluates the participant based on temporal relationship and his/her clinical judgment. The degree of certainty about causality will be graded using the categories below. In a clinical trial, the intervention and/or study procedures must always be suspect.

- **Related –** The AE is known to occur with the study intervention, there is a reasonable possibility that the study intervention caused the AE, or there is a temporal relationship between the study intervention and event. Reasonable possibility means that there is evidence to suggest a causal relationship between the study intervention and the AE.
- **Not Related –** There is not a reasonable possibility that the administration of the study intervention caused the event, there is no temporal relationship between the study intervention and event onset, or an alternate etiology has been established.

8.3.2.3 EXPECTEDNESS

The Principal Investigator and Chief Safety Officer will be responsible for determining whether an adverse event (AE) is expected or unexpected. An AE will be considered unexpected if the nature, severity, or frequency of the event is not consistent with the risk information previously described for the study intervention.

8.3.3 TIME PERIOD AND FREQUENCY FOR EVENT ASSESSMENT AND FOLLOW-UP

- Events that are judged to be “related” to the SAFE Loop should be, at a minimum, temporally linked to the filing of an incident report for a Target Medication Event during the intervention period in an intervention nursing unit.
- Alternatively, medication errors that are judged to be “related” to the SAFE Loop should generally occur during the latter part of the “SAFE Loop” period (when the intervention designed to prevent medication errors is designed and implemented) or the “follow-on” intervention period. It should occur in an intervention nursing unit and match the definition of a Target Medication Event, as well as have features suggesting that they were caused by the changes on the nursing unit made in response to the SAFE Loop.

All AEs not meeting the criteria for SAEs will be captured on the appropriate case report form (CRF). Information to be collected includes event description, time of occurrence, an assessment of severity, relationship to study (assessed only by those with the training and authority to make this assessment), and time of resolution/stabilization. All AEs occurring while on study must be documented appropriately regardless of relationship. All AEs will be followed to adequate resolution.

8.3.4 ADVERSE EVENT REPORTING

The study team will report any potential or actual adverse events to the Cedars-Sinai Institutional Review Board and the external DSM within 7 days, to allow time to begin to investigate the event. A final report adjudicating the nature and severity of the event and relationship to the intervention will be provided to the IRB and external DSM within 30 days.

The team will respond to any adverse events with a written mitigation and prevention plan to avoid recurrence, and consider whether doing so may be beneficial following any potential adverse events. This plan will be developed within 60 days, to allow for a thorough understanding of circumstances leading up to the event.

8.3.5 SERIOUS ADVERSE EVENT REPORTING

If an event may meet criteria for being serious, the study team will report it to the Cedars-Sinai Institutional Review Board and the external DSM within 24 hours, while the investigation proceeds. Following the final adjudication of the event, the report will also be submitted to the AHRQ Project Officer.

8.3.6 REPORTING EVENTS TO PARTICIPANTS

In the event of disclosures of protected health information outside the research team, we will adhere with HIPAA and other regulations regarding notifying affected patients. Events will be reported to participants if deemed appropriate by [name] (internal DSM), [name] (PI), the external DSM, or the Cedars-Sinai OHRP.

We will also report to nurses if individually identifying information of a sensitive nature is inadvertently disclosed outside the research team.

8.3.7 EVENTS OF SPECIAL INTEREST

Not Applicable

8.3.8 REPORTING OF PREGNANCY

Not Applicable

8.4 UNANTICIPATED PROBLEMS

8.4.1 DEFINITION OF UNANTICIPATED PROBLEMS (UP)

The Office for Human Research Protections (OHRP) considers unanticipated problems involving risks to participants or others to include, in general, any incident, experience, or outcome that meets **all** of the following criteria:

- Unexpected in terms of nature, severity, or frequency given (a) the research procedures that are described in the protocol-related documents, such as the Institutional Review Board (IRB)-approved research protocol and informed consent document; and (b) the characteristics of the participant population being studied;
- Related or possibly related to participation in the research (“possibly related” means there is a reasonable possibility that the incident, experience, or outcome may have been caused by the procedures involved in the research); and
- Suggests that the research places participants or others at a greater risk of harm (including physical, psychological, economic, or social harm) than was previously known or recognized.

This definition could include an unanticipated adverse device effect, any serious adverse effect on health or safety or any life-threatening problem or death caused by, or associated with, a device, if that effect, problem, or death was not previously identified in nature, severity, or degree of incidence in the investigational plan or application (including a supplementary plan or application), or any other unanticipated serious problem associated with a device that relates to the rights, safety, or welfare of subjects (21 CFR 812.3(s)).

8.4.2 REPORTING UNANTICIPATED PROBLEMS TO PARTICIPANTS

Unanticipated problems will be reported to participants if deemed appropriate by [name] (internal DSM), [name] (PI), the external DSM, or the OHRP.

9 STATISTICAL CONSIDERATIONS

9.1 STATISTICAL HYPOTHESES

Aim 1 Hypotheses:

1.1 The rate per 1000 patient-days at which nurses report incidents will increase more in nursing units engaged in the SAFE Loop than in units using the existing reporting system.

1.2 The number of system plus human factors per incident report will increase more in nursing units engaged in the SAFE Loop than in units using the existing reporting system. (Primary outcome for Aim 1)

Aim 2 Hypotheses:

2.1 Nurses' perceptions of feedback and communication about error on the nursing unit will improve more in nursing units engaged in the SAFE Loop than in units using the existing reporting system. (Primary outcome for Aim 2)

2.2 Nurses' perceptions of the frequency with which events are reported on the nursing unit will increase more in nursing units engaged in the SAFE Loop than in units using the existing reporting system.

Aim 3 Hypotheses:

3.1 The rate of medication events designated as high priorities will decline more in nursing units engaged in the SAFE Loop than in units using the existing reporting system. (Primary outcome for Aim 3)

3.2 The rate of medication events designated as high priorities and involving harm will decline more in nursing units engaged in the SAFE Loop than in units using the existing reporting system.

9.2 SAMPLE SIZE DETERMINATION

Aim 1:

On average per 6-month study period, each unit will provide 7,362 patient-days of care (294,470 pt-days/20/2) and submit 16.6 reports (665 reports/20/2). *H1.1.* The baseline rate is 2.26 incident reports per 1000 patient-days (665 reports/294,470). *H1.2.* Based on prior studies, the expected baseline number of system plus

Table 1: Minimum Detectable Difference in Outcome				
Implementation trend	Betw-Cluster Coeff. of Variation			
	0.01	0.05	0.10	0.20
1.1. Incident Reports per 1000 Patient-days				
Yes	1.241	1.277	1.392	1.851
No	0.794	0.815	0.877	1.115
1.2. System plus Human Factors per Incident Report				
Yes	0.471	0.481	0.515	0.651
No	0.299	0.305	0.322	0.391

human factors is 0.70 per report.¹ **Table 1** presents the minimum detectable differences in outcomes as functions of the between-cluster coefficient of variation (CV) and the presence of implementation trend, using two-sided t-tests for Poisson rates with 80% power at 5% significance level. These differences would be meaningful to safety leaders, reflecting >35% increases in reporting rates and enhanced detection of the multiple contributing multiple factors that are typically involved in every error.

Aim 2:

Power calculations are the same for both composite outcome measures. The baseline percentages of positive responses are 75% (H2.1) and 72% (H2.2). We assume 85% of 1980 nurses will be eligible and a 60% response rate (50.5 responses per nursing unit per deployment). We also assume a discrete uniform distribution for each composite measure with only four possible values (0%, 33%, 66%, 100%) per nurse because each measure contains 3 items. Therefore, we assume standard deviation (SD) equal to 37%, and a between-cluster coefficient of variation of 0.65 as recommended by Campbell and Walters.² The **Table** presents the minimum detectable difference in the percentage of positive responses as a function of the intra-cluster correlation (ICC) and presence of implementation trend, using a two-sided t-test for Normal means with 80% power at 5% significance level. Based on prior studies, a meaningful difference in the percentage of positive responses is 8.6 percentage points (pp).³ Missing data patterns will be examined using the method proposed by Little⁴ if the data is found to be not missing at completely random, missing values will be imputed with values drawn from fully conditional specifications using the multivariate imputation by chained equations (MICE) algorithm,^{5,6} with the number of imputed datasets chosen such that the maximum loss of efficiency of 5%.⁷ The plausibility of imputed values will be checked by corresponding diagnostics. The outlined statistical analysis will be performed for each imputed dataset and results will be pooled. All hypotheses will be two-sided at 5% significance level. Calculations will be performed using R-package, version 3.5.3.

Implementation trend	Intra-cluster Correlation			
	0.01	0.05	0.10	0.20
Yes	10pp*	11pp	12pp	13pp
No	7pp	8pp	10pp	11pp

¹ [name] TK, Bell DS, Paddock SM, Hilborne LH. Contributing factors identified by hospital incident report narratives. Qual Saf Health Care. Oct 2008;17(5):368-372.

² Campbell MJ, Walters SJ. How to design, analyse and report cluster randomised trials in medicine and health related research. John Wiley & Sons; 2014.

³ Campione J, Famolaro T. Promising Practices for Improving Hospital Patient Safety Culture. Jt Comm J Qual Patient Saf. Jan 2018;44(1):23-32.

⁴ Little RJ. A test of missing completely at random for multivariate data with missing values. Journal of the American Statistical Association. 1988;83(404):1198-1202.

⁵ Audigier, V., White, I., Jolani, S. Debray, T., Quartagno, M., Carpenter, J., van Buuren, S. and Resche-Rigon, M. Multiple imputation for multilevel data with continuous and binary variables. Statistical Science 2018;33(2):160-183

⁶ Resche-Rigon, M. and White, I. R. Multiple imputation by chained equations for systematically and sporadically missing multilevel data. Statistical Methods in Medical Research 2018; 27(6): 1634-1649

⁷ White IR, Royston P, Wood AM. Multiple imputation using chained equations: Issues and guidance for practice. Stat Med. 2011 Feb 20;30(4):377-99.

Aim 3:

Table 3 presents the minimum detectable difference in event rates as functions of between-cluster coefficient of variation and implementation trend using a two-sided t-test for Poisson rates with 80% power at 5% significance level. A difference of 0.50 events per 1000 patient days is clinically meaningful, representing the avoidance of 147 events and 116 harmful events per year hospital-wide.

Table 3: Minimum Detectable Difference in Outcome				
Implementation trend	Betw-Cluster Coeff of Variance			
	0.01	0.05	0.10	0.20
3.1 Target Event Rate				
Yes	0.766	0.929	1.292	2.108
No	0.516	0.631	0.886	1.474
3.2 Harmful Event Rate				
Yes	0.322	0.335	0.373	0.486
No	0.220	0.230	0.257	0.340

Qualitative Interviews:

Qualitative methods do not involve statistical tests or rely on calculations of statistical power. Instead, we provide a rationale for the proposed sample size and describe analytical methods.

After SAFE Loop implementation, we will conduct one-on-one in-person interviews with 10 Nursing Unit Managers and 22 frontline nurses. This sample size will enable us to perform purposive sampling to acquire broad representation by randomization block (there are 5 blocks), study group (there are four groups, with five nursing units per group – one from each block; half of the groups receive the intervention), and nursing unit (there are 10 nursing units that will be randomized to the SAFE Loop arm). Thus, we will interview one nurse manger and two nurses from each study nursing unit, about 6 per block, and 16 per group.

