B) *Patients:* Cedars-Sinai has 49,000 inpatient, 7,700 observation, and 58,000 emergency department encounters in a typical year, resulting in a total of 294,470 patient-days of care in study nursing units per year. Under Aim 1, incident reports for about 1,663 patients will be analyzed. Under Aim 3, medical records for 1,520 eligible hospitalizations during the SAFE Loop study period will be randomly sampled and analyzed.

Description of Sites/Facilities Enrolling Participants:

20 Cedars-Sinai acute care nursing units in the main Medical Center

Description of Study Intervention:

We will conduct a cluster RCT to compare nursing units that implement the SAFE Loop, a system-level change in incident reporting, with nursing units that continue to use the existing reporting system. The Safety Action Feedback and Engagement (SAFE) Loop has three phases: Engagement, Fact-finding, and Action & Feedback.

Across the three phases, the SAFE Loop has five Key Attributes: (1) obtaining input from nurses on which problems to address; (2) focusing on selected high-priority events, (3) prompting nurses to report the high-priority events for a designated period and write more informative reports; (4) following standardized investigative procedures to integrate information from sources internal and external to CSMC, and (5) providing feedback to nurses about safety problems and mitigation plans. During all phases, the SAFE Loop Team collaborates with frontline nurses and Unit Managers. (See schemata in Section 1.2)

[figure not shown]
Study Duration: 60 months
Participant Duration: 24 weeks

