9.4.2 ANALYSIS OF THE PRIMARY EFFICACY ENDPOINT(S)

Aim 1 Analyses:

Descriptive Analysis: We will perform descriptive analyses of reporting practices during the baseline periods and intervention periods, stratified by study arm. We will calculate rates of reported Target Medication Events and total reported medication events per 1000 patient-days (# of reports*1000/# of patient-days). Next, we will calculate the percentages of reported incidents in each NCC MERP category and the percentages of reports for which preventability could be determined. Finally, we will calculate

the number of contributing system, human, and patient factors per report and describe the types of factors reported.

Statistical Analyses: We will compare changes over time between study arms for: (a) rate of incident reports per 1000 patient-days, and (b) number of system plus human factors per report. Multivariable Poisson regression models will be fitted with response variables as (a) number of reports per patient, with offset given by the length of stay divided by 1000; and (b) number of system plus human factors per report. For both models, the main hypothesis is whether there is an interaction between study arm and time period (baseline, post-intervention). Nursing units will be divided between two implementation steps, creating the possibility of an implementation trend. Therefore, a three-way interaction among study arm, time period, and implementation step (Step 1: Group 1 and 2, Step 2: Group 3 and 4) will be tested. If this is statistically significant, results will be presented separately for each implementation step. Otherwise, implementation step will be an additive effect. Random effects will describe nursing units and models will adjust for demographics, Elixhauser comorbidity index, and primary payer (collected under Aim 3). All hypotheses will be two-sided at 5% significance level. Calculations will be performed in R-package, version 3.5.3.

Aim 2 Analyses:

Descriptive Analysis: We will calculate survey response rates, examine respondent characteristics (years worked in current profession, hospital, and current nursing unit and hours worked per week), and describe outcome measures (overall scores and composite measures) during each study period, stratified by study arm.

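### Table 1 (Aim 1) gives detectable differences for a one-period comparison of arms, but the planned test is the arm-by-period interaction, which at low between-unit variation needs a larger effect on the same volumes

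*Combined protocol and SAP*

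**What the plan says.** Section 9.2 (Aim 1) builds Table 1 on one volume per unit: "On average per 6-month study period, each unit will provide 7,362 patient-days of care", and each unit will "submit 16.6 reports (665 reports/20/2"). The baseline values are 2.26 reports per 1000 patient-days (H1.1) and 0.70 system plus human factors per report (H1.2). The differences are found "using two-sided t-tests for Poisson rates with 80% power at 5% significance level", for four between-cluster coefficients of variation (CV), with and without an implementation trend. For H1.2 without a trend the row reads 0.299, 0.305, 0.322 and 0.391.

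The hypothesis and the analysis concern change. Section 9.1 words the primary Aim 1 hypothesis as "The number of system plus human factors per incident report will increase more in nursing units engaged in the SAFE Loop" than in control units. Section 9.4.2 states that "the main hypothesis is whether there is an interaction between study arm and time period (baseline, post-intervention"), and adds: "Random effects will describe nursing units". Section 4.1 also describes the analyses as before-to-after comparisons between arms.

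On volume, the Synopsis says: "Under Aim 1, incident reports for about 1,663 patients will be analyzed". Section 9.4.2 plans "descriptive analyses of reporting practices during the baseline periods and intervention periods", and the design table in Section 6.3 assigns the follow-on period to Aim 3.

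**The concern.** A difference between arms in one period carries Poisson noise from two arm-period cells. A difference in change carries it from four. Using the baseline pays off when it removes large, stable differences between units. At a CV of 0.01 to 0.10 there is little to remove, so the change contrast adds more noise than it cancels.

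Table 1 is the only power statement for the primary Aim 1 outcome. If it describes a different contrast, a null result would be read as having had 80% power for a rise of about 0.30 factors per report when it did not. The report volume matters too: Section 9.2 implies 16.6 × 20 × 2 = 664 reports over two periods, while the Synopsis speaks of about 1,663 patients' reports.

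**Working it through.** **Inputs.** From Section 9.2: λ = 0.70 (H1.2) or 2.26 (H1.1); volume per unit per period E = 16.6 reports or 7.362 thousand patient-days; two-sided 5% and 80% power, so (1.960 + 0.842)² = 7.849. From Sections 4.1 and 9.3: 20 units, so K = 10 per arm, or 5 per arm within one implementation step.

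**Step 1. Reproduce Table 1.** The one-period, two-arm cluster-rate formula, solved for the difference d, is

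K = 1 + 7.849 × [(2λ + d)/E + CV²(λ² + (λ + d)²)] / d²

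Check for H1.2, no trend, CV 0.01, d = 0.299: (1.699/16.6 + 0.00015) × 7.849 / 0.299² = 9.0, so K = 10.

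| Row | K | Formula at CV 0.01 / 0.05 / 0.10 / 0.20 | Table 1 |
|---|---|---|---|
| H1.1 trend | 5 | 1.2405 / 1.277 / 1.392 / 1.851 | 1.241 / 1.277 / 1.392 / 1.851 |
| H1.1 no trend | 10 | 0.794 / 0.815 / 0.877 / 1.115 | 0.794 / 0.815 / 0.877 / 1.115 |
| H1.2 trend | 5 | 0.471 / 0.481 / 0.515 / 0.651 | 0.471 / 0.481 / 0.515 / 0.651 |
| H1.2 no trend | 10 | 0.299 / 0.305 / 0.322 / 0.391 | 0.299 / 0.305 / 0.322 / 0.391 |

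The cells are right for this formula. It has no baseline-period term.

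**Step 2. Same formula for the interaction.** With baseline and post-period volumes Eb and Ep, no change in the control arm and stable unit effects, the CV term cancels:

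K = 1 + 7.849 × [2λ/Eb + (2λ + d)/Ep] / d²

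H1.2, no trend, Eb = Ep = 16.6, d = 0.411: 7.849 × (3.211/16.6) / 0.411² = 8.99, so K ≈ 10.

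| Row | Table 1, CV 0.01 to 0.10 | Interaction | Table 1, CV 0.20 |
|---|---|---|---|
| H1.2 no trend | 0.299 to 0.322 | 0.411 | 0.391 |
| H1.2 trend | 0.471 to 0.515 | 0.637 | 0.651 |
| H1.1 no trend | 0.794 to 0.877 | 1.096 | 1.115 |
| H1.1 trend | 1.241 to 1.392 | 1.691 | 1.851 |

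Power at d = 0.299: the standard error is √[3.099/(16.6 × 9)] = 0.144, and 0.299/0.144 − 1.960 = 0.116, which gives 55%. At 0.305 and 0.322 it is 56% and 61%. Simulated t-tests on unit change scores (40,000 runs) gave 54% at 0.299 (CV 0.01), 60% at 0.322 (CV 0.10) and about 80% at 0.41.

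**Step 3. Log scale, as in a Poisson regression.** With d = 0.299 and 166 reports per arm-period, the expected factor totals are 116.2, 116.2, 116.2 and 165.8. The log ratio of ratios is ln(0.999/0.70) = 0.356, its standard error √(3/116.2 + 1/165.8) = 0.178, z = 1.99, and power 51%. At 0.305 and 0.322 power is 53% and 57%. The difference needed for 80% power is 0.447 without a trend and 0.693 with one.

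**Step 4. Sensitivity to volume (H1.2, no trend).** If 1,663 is a count of reports, then 1,663/40 = 41.6 per unit-period, and 1,663/20 − 16.6 = 66.5 if one period holds all the extra reports.

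| Reading | Eb / Ep | Needed (log scale) | Power at 0.299 to 0.322 |
|---|---|---|---|
| Section 9.2 volume | 16.6 / 16.6 | 0.41 (0.45) | 55 to 61% |
| 1,663 split evenly | 41.6 / 41.6 | 0.25 (0.26) | 91 to 94% |
| All extra in post-period | 16.6 / 66.5 | 0.31 (0.35) | 77 to 83% |
| All extra in baseline | 66.5 / 16.6 | 0.33 (0.33) | 72 to 78% |

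The stated 0.299, 0.305 and 0.322 reach 80% power at about 30, 29 and 26 reports per unit in each period (1,209, 1,164 and 1,050 in total). Table 1 was not computed on 1,663 reports: the one-period formula at 41.6 gives 0.182, 0.190 and 0.213 for CV 0.01, 0.05 and 0.10. If only intervention units file 35% more reports after implementation, the interaction needs 0.39.

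**The case against.** The strongest objection is that even the direction of the error depends on an unsettled volume. With 1,663 reports split evenly, Table 1 would be conservative. That count may also have a simple origin: the design table in Section 6.3 spans half of Year 1 plus Years 2 and 3, and 665 × 2.5 = 1,662.5. This stands as a limit on the size. It does not rescue the table, which was computed on 16.6 reports, and no section says which Aim 1 periods the extra reports would fill. A 12-month post-period (16.6 / 33.2) would need 0.346, still above the stated values at CV 0.01 to 0.10.

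Second, the shortfall is confined to low CV. With stable unit effects the two calculations cross at a CV of about 0.22 (H1.2 no trend), 0.19 (H1.2 trend), 0.19 (H1.1 no trend) and 0.17 (H1.1 trend). The units range from the emergency department to neonatal intensive care, so a very small CV is not an obvious expectation. This stands as well, but the plan adopts no expected CV and three of its four columns are 0.10 or below.

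Third, 0.41 is tied to one formula. Dropping its small-sample +1 gives 0.39, and the log scale gives about 0.45. A range of 0.39 to 0.45 is fair, and all of it lies above 0.322.

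Finally, no sample size or named H1.2 target rests on Table 1. That is accepted: the consequence lies in how the result is read.

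**Conclusion.** The concern holds. Table 1 answers a different question from the one Aim 1 will test, and no other section gives power for the interaction. On Section 9.2's volumes at a CV of 0.01 to 0.10, H1.2 without a trend needs about 0.41 (0.411/0.70 = +59%), or about 0.45 (+64%) on the log scale. The stated values are 0.299 to 0.322 (+43% to +46%), where power is 51% to 61% depending on scale. The remark in Section 9.2 about increases above 35% in reporting rates matches the smallest H1.1 cell (0.794/2.26 = 35.1%). It stays literally true, but the interaction's counterpart is 1.096/2.26, about +48%.

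These figures assume equal volumes in both periods, no change in the control arm, stable unit effects and no covariate adjustment. At a CV of 0.20 no material shortfall is claimed under those assumptions. Confidence is high on the mismatch. The size is conditional, because across the volume readings the detectable difference runs from about 0.25 to 0.41. This is a correction to the stated power and leaves the design unchanged.

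**What to change.** - Recalculate Table 1 for the arm-by-period interaction. State the baseline and post-period volumes per unit and the assumed between-period correlation of unit effects. The correlation matters: for H1.2 without a trend on 16.6 reports, 0.8 or 0.5 gives about 0.42 or 0.43 at CV 0.10, and about 0.44 or 0.48 at CV 0.20.
- Reconcile the 665 reports per year in Section 9.2 with the 1,663 in the Synopsis, and say which periods supply Aim 1 reports.
- Check whether Table 3, which names the same kind of test for Aim 3, has the same mismatch. Its inputs are not stated, so no corrected values are offered here.

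A baseline-adjusted or common-baseline model with a small-sample reference distribution is an option for the sponsor and is not required.

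The cost is one recalculated table and one reconciled count. The downside is less favourable figures at CV 0.01 to 0.10 if the 16.6-report volume stands.

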9.3 POPULATIONS FOR ANALYSES

The trial will randomize 20 nursing units to two arms: (1) the SAFE Loop, and (2) the existing reporting system (control). All analyses will compare data between these two arms.

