Assessment of Survey Measurement Properties: To evaluate the two selected composite measures' internal consistency, we will calculate Cronbach's α using data from baseline survey. To assess construct validity and convergent validity, respectively, we will evaluate associations (Pearson correlation coefficients) between scores on the composite measures and: (1) the full Hospital SOPS, and (2) incident reporting rates at the nursing unit level. To assess responsiveness, we will compare scores from baseline and follow-up surveys among nurses in the SAFE Loop arm (paired t-tests). If the composite measures do not demonstrate good internal consistency, construct, and convergent validity, we will use the full Hospital SOPS.

Statistical Analyses: We will compare changes over time between study arms for Feedback and Communication About Error and Frequency of Events Reported. Multivariable Normal regression models will be fitted for both endpoints and we will test hypotheses similarly to Aim 1. We will adjust for nurse characteristics from the AHRQ survey: years working in this hospital, years worked in current nursing unit, and hours worked per week. We will perform subgroup analyses by years of experience in current profession, because experience has been associated with medication error rates.⁵⁹

Aim 3 Analyses:

Descriptive Analysis: We will calculate rates of preventable ADEs and potential ADEs per 1,000 patient-days, both overall and for the Target Medication Events for the Group 1 and 3 nursing units. We will describe the severity of the events, medication classes, errors, clinicians involved, and stages in drug therapy.

Statistical Analysis: We will compare changes over time between study arms for rates of (a) Target Medication Events per 1000 patient-days and (b) harmful Target Medication Events per 1000 patient-days. Multivariable Poisson models will be fitted with response variable as the number of (a) target medication events and (b) harmful medication events, with offset the length of stay divided by 1000

days. We will test hypotheses similarly to under Aim 1. Model covariates will include patient demographics, biological sex, Elixhauser comorbidity index, and insurance payer.

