10 SUPPORTING DOCUMENTATION AND OPERATIONAL CONSIDERATIONS

10.1 REGULATORY, ETHICAL, AND STUDY OVERSIGHT CONSIDERATIONS

10.1.1 INFORMED CONSENT PROCESS

10.1.1.1 CONSENT/ASSENT AND OTHER INFORMATIONAL DOCUMENTS PROVIDED TO PARTICIPANTS

We are requesting a waiver of informed consent for implementation of the SAFE Loop intervention (both nurse and patients) and data collection procedures for Aim 1 (incident reports, both nurses and patients), and Aim 3 (adverse medication events, patients).

For nurses participating in Aim 2 (surveys) we are requesting a waiver of consent documentation. As the survey is via REDCap and is not collecting any identifiable information, requiring a signature would be the only link to a subject's identify. An information sheet will be provided with full consent information. Agreeing to complete and submit the survey will indicate their consent to participate.

For nurses participating in the qualitative interviews of implementation, we will provide consent forms describing in detail the study procedures and risks to the participant. Written documentation of informed consent is required prior to starting intervention/administering study intervention. The following consent materials are submitted with this protocol.

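### The Aim 2 detectable-difference table does not follow from its stated inputs; the stated test gives about 8.5–23 pp with 10 units per arm and 13–35 pp with 5, not 7–11 and 10–13 pp

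*Combined protocol and SAP*

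**What the plan says.** The Aim 2 part of Section 9.2 gives the "minimum detectable difference in the percentage of positive responses as a function of the intra-cluster correlation (ICC) and presence of implementation trend". The calculation is for a t-test of Normal means at the two-sided 5% level, and power is set to 80%. Its inputs are an SD of 37%, 50.5 responses per unit per deployment, and "a between-cluster coefficient of variation of 0.65". It adds that "a meaningful difference in the percentage of positive responses is 8.6 percentage points (pp").

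| Implementation trend | ICC 0.01 | 0.05 | 0.10 | 0.20 |
|---|---|---|---|---|
| Yes | 10 pp | 11 pp | 12 pp | 13 pp |
| No | 7 pp | 8 pp | 10 pp | 11 pp |

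Section 9.3 states: "The trial will randomize 20 nursing units to two arms". Section 4.1 randomizes 5 intervention and 5 control units at a time. Section 9.4.2 tests a three-way interaction of arm, period and implementation step, and adds: "If this is statistically significant, results will be presented separately for each implementation step". Section 9.1 makes H2.1 the primary outcome of Aim 2.

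**The concern.** With only 20 units, the number of clusters should dominate the calculation. At ICC 0.20 and about 50 nurses per unit the design effect is near 11, yet the printed difference rises only from 7 to 11 pp between ICC 0.01 and 0.20. The trend row rises only from 10 to 13 pp.

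The table is what a reader will use to judge whether Aim 2 could have found a meaningful effect. Two no-trend cells (7 and 8 pp) lie under 8.6 pp, so the plan appears able to detect it up to an ICC of at least 0.05. If those cells are too small, a null result on a primary outcome would be read against sensitivity that the calculation does not support.

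**Working it through.** **Inputs**
- Responses per unit: m = 1980 × 0.85 × 0.60 / 20 = 50.49. This reproduces the plan's 50.5.
- SD = 37 pp. A discrete uniform on 0, 33.3, 66.7 and 100 has SD 37.27, so this also reproduces.
- Units per arm: K = 10 (Section 9.3). For the trend row, K = 5, inferred from Sections 4.1 and 9.4.2.
- Cluster-size CV: the nurse counts in Section 5.1 have mean 99 and SD 31.4, so CV = 0.317. The range 0 to 0.65 is shown.
- Multiplier c for 80% power, two-sided 5%, noncentral t on 2K − 2 df: 2.963 (18 df) and 3.201 (8 df). The normal value is 2.802.

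**Check of the reading on Aim 1.** For H1.1, take d = c·√{[(r₀ + r₁)/y + CV²(r₀² + r₁²)]/K} with r₀ = 2.26, r₁ = r₀ + d and y = 7.362 thousand patient-days. K = 10 gives 0.797, 0.818, 0.881, 1.119 (printed 0.794, 0.815, 0.877, 1.115). K = 5 gives 1.271, 1.309, 1.428, 1.905 (printed 1.241, 1.277, 1.392, 1.851). The first row agrees to under 1% and the second to 2–3%, which supports 10 and 5 units per arm.

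**Aim 2**
- DEFF = [1 + (m − 1)ρ] / [1 − CV²·λ(1 − λ)], with λ = mρ/(mρ + 1 − ρ)
- SE = 37·√(2·DEFF/(K·m))
- MDD = c × SE

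Example, ρ = 0.05, K = 10, CV = 0: DEFF = 1 + 49.49 × 0.05 = 3.47; SE = 37·√(6.95/504.9) = 4.34; MDD = 2.963 × 4.34 = 12.9 pp. The table prints 8.

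| | ICC 0.01 | 0.05 | 0.10 | 0.20 |
|---|---|---|---|---|
| No trend, printed | 7 | 8 | 10 | 11 |
| K = 10, CV 0.317 | 8.5 | 13.0 | 16.9 | 22.9 |
| K = 10, CV 0 to 0.65 | 8.4–8.9 | 12.9–13.4 | 16.8–17.3 | 22.8–23.1 |
| K = 10, normal, CV 0 | 8.0 | 12.2 | 15.9 | 21.5 |
| Trend, printed | 10 | 11 | 12 | 13 |
| K = 5, CV 0.317 | 13.0 | 19.9 | 25.9 | 34.9 |
| K = 5, CV 0 to 0.65 | 12.9–13.5 | 19.6–20.5 | 25.7–26.4 | 34.8–35.3 |
| K = 5, normal, CV 0 | 11.3 | 17.2 | 22.5 | 30.5 |
| Power for 8.6 pp, K = 10, CV 0.317 | 81% | 46% | 30% | 18% |

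The cruder design effect 1 + [(1 + CV²)m − 1]ρ with CV 0.65 gives larger values: up to 26.9 pp (K = 10) and 41.1 pp (K = 5).

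**Floor with unlimited nurses.** As m grows, MDD tends to 37·c·√(2ρ/K). For K = 10 that is 11.0, 15.5 and 21.9 pp at ICC 0.05, 0.10 and 0.20 (normal: 10.4, 14.7, 20.7). The printed 8, 10 and 11 lie below it, so no response rate or cluster-size CV can produce them.

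**The two rows against each other.** Halving K multiplies the MDD by at least √2 = 1.41 (1.53 with cluster df). The printed ratios fall from 10/7 = 1.43 to 13/11 = 1.18; allowing for rounding, the last is at most 13.5/10.5 = 1.29. In the Aim 1 and Aim 3 tables every cell lies between 1.43 and 1.66.

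**The 0.65.** As a CV of the outcome it implies a between-unit SD of 0.65 × 75 = 48.8 pp. That exceeds the total SD of 37 and also √(75 × 25) = 43.3, the largest SD that a 0–100 score with mean 75 can have. It appears to be a cluster-size CV.

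**A possible source (inference only).** Interchanging clusters and cluster size, with 50 clusters per arm, CV 0.65 and normal quantiles, gives 6.97, 8.30, 9.55, 11.48 for size 10 and 9.55, 10.53, 11.54, 13.14 for size 5. All eight cells match after rounding.

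**The planned contrast.** For a change score, var(unit change) = 2·37²·[ρ(1 − a) + (1 − ρ)(1 − n)/m], where a is the unit-level and n the within-nurse correlation between surveys. Both are assumed here; the plan gives neither. For K = 10, 18 df, from ICC 0.01 to 0.20:
- a = 1.0, n = 0.5: 6.9 to 6.2 pp
- a = 0.9, n = 0.5: 7.2 to 11.6 pp
- a = 1.0, n = 0: 9.7 to 8.7 pp
- a = 0.9, n = 0: 10.0 to 13.1 pp
- a = 0.8, n = 0: 10.2 to 16.4 pp
- a = n = 0: 11.9 to 32.2 pp

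**The case against.** The strongest reply is that the planned Aim 2 analysis is an arm-by-period interaction, not a comparison of follow-up scores alone. Under the first five correlation pairs above, its power for 8.6 pp at ICC 0.05 runs from 54% to 95%. With a = 0.91 and n = 0.45 it gives 7.5, 8.5, 9.5 and 11.3 pp, which matches the no-trend row. So that row could be about right for the analysis that will be run, and this stands as a limit on the point. It does not rescue the table. Section 9.2 states no such correlation, and the same pair gives 11.5, 12.9, 14.5 and 17.3 pp for 5 per arm against a printed 10, 11, 12 and 13. A grid of pairs found none that fits both rows; the best joint fit misses a cell by 1.1 pp. Within-nurse credit also needs linked responses, on which the documents disagree.

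Other reservations are fair:
- The 5-per-arm reading is inferred, and the note to the marker on the 10 pp cell is not in the text available to us.
- The CV of 0.317 comes from staff counts, not respondents, but across 0 to 0.65 results move by only about 0.7 pp.
- The interchange explanation is fragile. With 50.49 instead of 50 clusters, two trend cells become 10.48 and 11.49 and round differently.
- Six of the eight printed cells already exceed 8.6 pp. Section 8.1 gives that figure a range of 6.5–10.6, for overall survey scores rather than this composite.

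**Conclusion.** The point holds. For the two-sample test described in Section 9.2, all eight printed values are too small, even with normal quantiles and equal cluster sizes. At ICC 0.20 the understatement is a factor of 22.9/11 = 2.1 without trend and 34.9/13 = 2.7 with trend.

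Against the plan's own 8.6 pp, the no-trend row shows detection at ICC 0.01 and 0.05. The stated test reaches 8.6 pp only up to an ICC of about 0.010 (0.008 to 0.011 over cluster-size CVs from 0.65 down to 0). At ICC 0.05 it needs about 13 pp.

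This rests on 10 units per arm, 5 per arm for the trend row, cluster-based df and a follow-up-only comparison. It shows that the table cannot be obtained from its stated inputs. It does not establish the sensitivity of the arm-by-period analysis, which depends on unstated correlations. The mislabelling of the 0.65 and the inconsistency between the rows do not depend on that choice.

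**What to change.** 1. Recompute the table with 10 units per arm (and 5, if that is what trend means), about 50.5 responses per unit, cluster-based df and a cluster-size CV taken from the unit list (about 0.32, with a range for uneven response).
2. State the formula and how implementation trend enters it.
3. If the table is meant for the arm-by-period contrast, state the assumed between-survey unit correlation and any within-nurse correlation, and show a range.
4. Before taking within-nurse credit, settle whether responses are linked. Section 9.4.2 plans paired t-tests and Section 10.1.9.1 describes surveys as identifiable, but Section 10.1.1.1 says the survey "is not collecting any identifiable information".
5. Restate the ICC values at which 8.6 pp is detectable, and correct the label of the 0.65.

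The cost is one restated table with its assumptions and one label. The figures for the stated test become less favourable. The number of units, the design and the data collection need not change.
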